## 9.1 Efficacy Assessment

### 9.1.1 Clinical Outcomes for EOT and TOC

The clinical outcomes will be assessed by the investigator according to the following criteria established for each infection site at EOT and TOC. In case treatment duration is extended beyond 14 days, an additional clinical outcome will be assessed on Day 14. The clinical outcomes will be entered in the electronic case report form (eCRF).

#### 9.1.1.1 HABP/VABP/HCABP

- **Clinical Cure:** Resolution or substantial improvement of baseline signs and symptoms of pneumonia including a reduction in SOFA score and clinical pulmonary infection score (CPIS), and improvement or lack of progression of chest radiographic abnormalities such that no antibacterial therapy is required for the treatment of the current infection.
- **Clinical Failure:** No apparent response to therapy; persistence or worsening of baseline signs and/or symptoms of pneumonia; reappearance of signs and/or symptoms of pneumonia; development of new signs and/or symptoms of pneumonia requiring antibiotic therapy other than, or in addition to, study treatment therapy; progression of chest radiographic abnormalities; or death due to pneumonia.
- **Indeterminate:** Lost to follow-up such that a determination of clinical cure/failure cannot be made.

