#### **6.4.2 Missing Microbiological or Clinical Outcome**

For clinical and microbiological outcomes, subjects who are lost to follow-up or have missing or "indeterminate" outcomes will be included in the denominator as indeterminate for cure/eradication rate, i.e., considered as not responders. If judged by the investigator that a subject died due to pneumonia, BSI/sepsis or cUTI, the clinical outcome will be considered as clinical failure after the event of death. If a subject died due to other reasons, the clinical outcome will be considered as "indeterminate" after death.

For clinical outcome, if a subject received additional antibiotics for target disease (i.e., baseline infection) before the target date, the outcome will be considered as "clinical failure". If a subject did not receive additional antibiotics for target disease before the target date, the outcome will be considered as "indeterminate".

Missing values for other individual data points will remain as missing unless otherwise specified. All analysis will be based on observed case unless otherwise stated.

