#### 9.1.1.2 cUTI

- **Clinical Cure:** Resolution or substantial improvement of baseline signs and symptoms of cUTI, or return to preinfection baseline if known, such that no antibacterial therapy is required for the treatment of the current infection.
- **Clinical Failure:** No apparent response to therapy; persistence or worsening of baseline signs and/or symptoms of cUTI; or reappearance of signs and/or symptoms of cUTI; development of new signs and/or symptoms of cUTI requiring antibiotic therapy other than, or in addition to, study treatment therapy; or death due to cUTI.
- **Indeterminate:** Lost to follow-up such that a determination of clinical cure/failure cannot be made.

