#### 9.1.1.3 BSI/Sepsis

- **Clinical Cure:** Resolution or substantial improvement of baseline signs and symptoms including a reduction in SOFA score, such that no antibacterial therapy is required for the treatment of BSI/sepsis. Subjects with bacteremia must have eradication of bacteremia caused by the Gram-negative pathogen.
- **Clinical Failure:** No apparent response to therapy; persistence or worsening of baseline signs and/or symptoms, reappearance of signs and/or symptoms;

development of new signs and/or symptoms requiring antibiotic therapy other than, or in addition to, study treatment therapy; or death due to BSI/sepsis.

- **Indeterminate:** Lost to follow-up such that a determination of clinical cure/failure cannot be made.

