#### **9.1.2.1 HABP/VABP/HCABP**

- **Sustained Clinical Cure:** Continued resolution or substantial improvement of baseline signs and symptoms of pneumonia, such that no antibacterial therapy is required for the treatment of pneumonia in a subject assessed as cured at TOC.
- **Relapse:** Recurrence of signs and/or symptoms of pneumonia, appearance of new signs and/or symptoms of pneumonia, or new chest radiographic evidence of pneumonia in a subject assessed as cured at TOC.
- **Indeterminate:** Lost to follow-up such that a determination of clinical sustained cure/relapse cannot be made, or subject received additional antibacterial therapy for the treatment of the current infection. Indeterminate at TOC will be carried forward.
- **Clinical Failure:** Clinical failure at TOC will be carried forward regardless of lost to follow-up.

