### 9.2.2 Supplementary Clinical Outcomes for EOT and TOC

#### 9.2.2.1 HABP/VABP/HCABP

- **Clinical Cure:** Resolution or substantial improvement of baseline signs and symptoms of pneumonia including a reduction in SOFA and CPIS scores, and improvement or lack of progression of chest radiographic abnormalities such that no antibacterial therapy is required for the treatment of the current infection.
- **Clinical Failure:** No apparent response to therapy; persistence or worsening of baseline signs and/or symptoms of pneumonia; reappearance of signs and/or symptoms of pneumonia; development of new signs and/or symptoms of pneumonia requiring more than 48 hours of antibiotic therapy other than, or in addition to, study treatment therapy; progression of chest radiographic abnormalities; or death due to pneumonia or death after Day 4 (including) regardless of the reason. If EOT is clinical failure, TOC is also clinical failure.
- **Indeterminate:** Lost to follow-up due to death other than pneumonia at Days 1, 2 or 3, withdrawal, or no assessment.

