### **9.3.1 Primary Analyses for the Primary Efficacy Endpoint**

For the CR Micro-ITT population, the following analysis will be performed.

The clinical outcomes at TOC will be summarized and clinical cure rates and its 95% CIs will be calculated by treatment group (cefiderocol or BAT) for subjects with HABP/VABP/HCABP or BSI/sepsis, separately. The clinical response rate will be calculated as the proportion of subjects whose clinical outcome is clinical cure at TOC.

The microbiological outcomes at TOC will be summarized and microbiological eradication rates and its 95% CIs will be calculated by treatment group (cefiderocol or BAT) for the subjects with cUTI. The microbiological response rate will be calculated as the proportion of subjects whose all of baseline Gram-negative uropathogen(s) are eradicated at TOC.

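### The primary clinical outcome at TOC has no firm rule for patients rescued with other antibiotics, so a rescued patient can be counted as a cure

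*SAP*

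**What the plan says.** **Primary definition.** Under SAP 9.1.1 the investigator rates clinical outcome at EOT and again at TOC. Pneumonia cure (9.1.1.1) needs better signs and symptoms, lower SOFA and CPIS scores and no radiographic progression, "such that no antibacterial therapy is required for the treatment of the current infection". BSI/sepsis cure (9.1.1.3) is built the same way, "such that no antibacterial therapy is required for the treatment of BSI/sepsis", and adds eradication for bacteremic patients. The cUTI clinical definition (9.1.1.2) has the same form, "or return to preinfection baseline if known, such that no antibacterial therapy is required for the treatment of the current infection", but is a secondary endpoint. In all three, the indeterminate category covers only loss to follow-up.

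**Primary analysis.** SAP 9.3.1: "The clinical response rate will be calculated as the proportion of subjects whose clinical outcome is clinical cure at TOC".

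**Patients who fail.** Protocol 6.2.4 permits adding or substituting antibiotics once a patient is judged a clinical or microbiologic failure, with an EOT assessment at that point. Protocol 7.13 keeps such patients in the study through TOC and later visits.

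**Rules stated elsewhere.** The supplementary clinical outcome (SAP 9.2.2.1, repeated for the other two sites) adds: "If EOT is clinical failure, TOC is also clinical failure". The Follow-up outcome (SAP 9.1.2.1) is indeterminate if the patient was lost to follow-up, "or subject received additional antibacterial therapy for the treatment of the current infection". The microbiological outcome (SAP 9.1.3) is also indeterminate after additional therapy.

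**SAP 6.4.2**, headed Missing Microbiological or Clinical Outcome, has two paired sentences. The first says that "if a subject received additional antibiotics for target disease (i.e., baseline infection) before the target date, the outcome will be considered as" clinical failure. The second reads: "If a subject did not receive additional antibiotics for target disease before the target date, the outcome will be considered as" indeterminate.

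**The concern.** The primary rate should describe cure on the assigned treatment. As written, cure at TOC is a statement about the patient's state at one visit and says nothing of how that state was reached. A patient who failed study treatment, was switched and got better on other drugs can meet every element of the definition, and the cure is then credited to the randomized arm.

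The trial is open-label, and both the decision to switch and the TOC rating belong to the investigator, so any leniency need not be equal in the two arms. The one sentence that might prevent this, in SAP 6.4.2, can be read in two ways. Two programmers working from the same SAP could produce different primary cure counts.

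**Working it through.** **1. One patient under each rule.** Take a pneumonia patient rated failure at EOT and given another systemic Gram-negative antibiotic for that pneumonia. By TOC the course is over, SOFA and CPIS are lower, the radiograph has not progressed, and the investigator records cure.

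| Rule | Result at TOC |
|---|---|
| SAP 9.1.1.1 with 9.3.1 | Cure |
| SAP 6.4.2 read as applying to missing outcomes only | Cure (a rating exists) |
| SAP 6.4.2, first sentence read as an override | Failure |
| SAP 9.2.2.1 (supplementary) | Failure, carried from EOT |
| SAP 9.1.3.1 (microbiological) | Indeterminate |

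**2. Does 6.4.2 settle it?** If both sentences applied to recorded ratings, patients with additional antibiotics would be failures and all others indeterminate, leaving no cures at all. The second sentence must therefore be limited to missing outcomes. The section heading suggests that the first sentence is limited in the same way, but the text does not say so.

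**3. Does the failure definition settle it?** Its phrase about lack of response could be taken to look back to EOT. The supplementary definition contains the same phrase and still adds the carry-forward sentence, so the phrase cannot be assumed to do that work.

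**4. Timing.** By SAP Table 6-1, TOC is 7 days after the last infusion, −2 to +2, that is 5 to 9 days. A rescue course begun at EOT can be over by TOC only if it lasts 9 days or less (7 or less at the nominal visit). Protocol 5.2 anticipates 7 to 14 days for study treatment. If rescue courses are similar, many would still be running at TOC, and those patients would not meet the cure definition.

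**5. Size per patient.** The plan's own figure reproduces: 150 × 2/3 = 100 on S-649266 (Protocol 9.2). Protocol 3.2.1 gives about 50% pneumonia and 20% BSI/sepsis. One reclassified patient moves a rate by 1/n. The last column assumes that 90% to 70% of randomized patients enter CR Micro-ITT, a range the documents do not give.

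| Stratum and arm | Planned n | Step | Step at 90% to 70% |
|---|---|---|---|
| Pneumonia, S-649266 | 150 × 0.5 × 2/3 = 50 | 2.0 points | 2.2 to 2.9 (n = 45 to 35) |
| Pneumonia, BAT | 150 × 0.5 × 1/3 = 25 | 4.0 points | 4.4 to 5.7 (n = 22.5 to 17.5) |
| BSI/sepsis, S-649266 | 150 × 0.2 × 2/3 = 20 | 5.0 points | 5.6 to 7.1 (n = 18 to 14) |
| BSI/sepsis, BAT | 150 × 0.2 × 1/3 = 10 | 10.0 points | 11.1 to 14.3 (n = 9 to 7) |

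**6. Illustration (assumed cure rate near 50%, Clopper-Pearson 95% intervals).** In pneumonia, three rescued patients counted as cures move S-649266 from 25/50 = 50.0% (35.5 to 64.5) to 28/50 = 56.0% (41.3 to 70.0), and BAT from 12/25 = 48.0% (27.8 to 68.7) to 15/25 = 60.0% (38.7 to 78.9).

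**7. Difference between arms (assumed).** If a share r of each arm is rescued and the proportion of those rated cure differs by 50 points between arms, the difference in cure rates shifts by r × 50 points. For r = 10% to 30% that is 5 to 15 points, in either direction.

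**The case against.** The best reply is that the text already leans towards failure. The failure definition includes new signs or symptoms calling for antibiotics beyond study treatment, without the 48-hour tolerance found in 9.2.2. Protocol 6.2.4 allows a switch only after a failure judgment. SAP 6.4.2 is not confined to blank fields, since it also assigns outcomes after death. Other analyses would expose rescued patients: the supplementary outcome, the composite of clinical and microbiological response (where additional therapy blocks a response), the survival and no-change composite (9.4.1.9), and possibly CR-ME, depending on the deviation specification. The primary analysis is descriptive, with no margin or between-arm test. The steps above are simply 1/n and would apply to any misclassified patient.

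Much of this limits the size, and that stands: the number of cases is unknown and timing keeps it down, and many investigators would rate such patients as failures. It does not close the gap. The antibiotic clause is attached to new signs or symptoms, so it need not reach a patient whose original infection simply failed to respond. A failure judgment at EOT does not bind the TOC rating. The other analyses leave the primary rate unchanged. The supplementary outcome also changes the TOC window to ±3 days, adds the 48-hour threshold and counts deaths from Day 4 whatever the cause, so it cannot isolate the effect of rescue.

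Counting recovery whatever drugs were used would be a defensible estimand if stated. It is not stated, and the microbiological and Follow-up rules point the other way.

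**Conclusion.** The concern holds. The primary clinical outcome at TOC lacks the EOT carry-forward that the SAP writes into its supplementary outcome, and SAP 6.4.2 does not clearly override a recorded cure. A rescued patient can therefore count as a primary cure in pneumonia or BSI/sepsis, and in the secondary cUTI clinical outcome.

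The total effect cannot be derived, because no rescue rate is given. Per patient it is 2 and 4 points in pneumonia and 5 and 10 points in BSI/sepsis (S-649266 and BAT) at planned sizes, and larger in CR Micro-ITT to the extent that population is smaller. The ambiguity itself rests on the text alone. The 70% to 90% range, the 50% cure rate and the rescue shares are assumptions used only to show scale. It should be fixed, because it affects the count in the primary analysis of an open-label trial with small strata.

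**What to change.** In SAP 9.1.1 state, for all three infection sites, that:

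1. clinical failure at EOT is clinical failure at TOC, as 9.2.2 already has it;
2. additional antibiotics (as defined in 6.8) for the baseline infection before the TOC assessment make the patient a non-cure at TOC, whatever rating was recorded.

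Both are needed. Carry-forward alone would miss patients switched for microbiologic failure only, or given other antibiotics between EOT and TOC.

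In SAP 6.4.2 limit the indeterminate sentence to missing outcomes. Report the unmodified investigator rating as a supplementary analysis, so that the effect of the rule is visible.

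The cost is SAP wording and one derived variable. EOT outcomes and all antibiotics up to EOS are already in the eCRF. Cure rates may fall slightly. Because the rule changes how the primary endpoint is derived in an open-label study, it should be settled before database lock and listed in SAP 15.

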#### 9.1.1.2 cUTI

- **Clinical Cure:** Resolution or substantial improvement of baseline signs and symptoms of cUTI, or return to preinfection baseline if known, such that no antibacterial therapy is required for the treatment of the current infection.
- **Clinical Failure:** No apparent response to therapy; persistence or worsening of baseline signs and/or symptoms of cUTI; or reappearance of signs and/or symptoms of cUTI; development of new signs and/or symptoms of cUTI requiring antibiotic therapy other than, or in addition to, study treatment therapy; or death due to cUTI.
- **Indeterminate:** Lost to follow-up such that a determination of clinical cure/failure cannot be made.

#### 9.1.1.3 BSI/Sepsis

- **Clinical Cure:** Resolution or substantial improvement of baseline signs and symptoms including a reduction in SOFA score, such that no antibacterial therapy is required for the treatment of BSI/sepsis. Subjects with bacteremia must have eradication of bacteremia caused by the Gram-negative pathogen.
- **Clinical Failure:** No apparent response to therapy; persistence or worsening of baseline signs and/or symptoms, reappearance of signs and/or symptoms;

development of new signs and/or symptoms requiring antibiotic therapy other than, or in addition to, study treatment therapy; or death due to BSI/sepsis.

- **Indeterminate:** Lost to follow-up such that a determination of clinical cure/failure cannot be made.

### **9.1.2 Clinical Outcomes for Follow-up**

The clinical outcomes will be assessed by the investigator according to the following criteria established for each infection site at FU. The clinical outcomes will be entered in the eCRF.

#### **9.1.2.1 HABP/VABP/HCABP**

- **Sustained Clinical Cure:** Continued resolution or substantial improvement of baseline signs and symptoms of pneumonia, such that no antibacterial therapy is required for the treatment of pneumonia in a subject assessed as cured at TOC.
- **Relapse:** Recurrence of signs and/or symptoms of pneumonia, appearance of new signs and/or symptoms of pneumonia, or new chest radiographic evidence of pneumonia in a subject assessed as cured at TOC.
- **Indeterminate:** Lost to follow-up such that a determination of clinical sustained cure/relapse cannot be made, or subject received additional antibacterial therapy for the treatment of the current infection. Indeterminate at TOC will be carried forward.
- **Clinical Failure:** Clinical failure at TOC will be carried forward regardless of lost to follow-up.

#### **9.1.2.2 cUTI**

- **Sustained Clinical Cure:** Continued resolution or improvement of baseline signs and symptoms of cUTI, or return to preinfection baseline if known, in a subject assessed as cured at TOC.
- **Relapse:** Recurrence of signs and/or symptoms of cUTI, or appearance of new signs and/or symptoms of cUTI in a subject assessed as cured at TOC.
- **Indeterminate:** Lost to follow-up such that a determination of clinical sustained cure/relapse cannot be made, or subject received additional antibacterial therapy for the treatment of the current infection. Indeterminate at TOC will be carried forward.
- **Clinical Failure:** Clinical failure at TOC will be carried forward regardless of lost to follow-up.

#### **9.1.2.3 BSI/Sepsis**

- **Sustained Clinical Cure:** Continued resolution or substantial improvement of baseline signs and symptoms associated with reduction in SOFA score, such that no antibacterial therapy is required for the treatment of the subjects original BSI/sepsis in a subject assessed as cured at TOC.

- **Relapse:** Recurrence of signs and/or symptoms of BSI/sepsis, or appearance of new signs and/or symptoms of the subjects original BSI/sepsis in a subject assessed as cured at TOC.
- **Indeterminate:** Lost to follow-up such that a determination of clinical sustained cure/relapse cannot be made, or subject received additional antibacterial therapy for the treatment of the current infection. Indeterminate at TOC will be carried forward.
- **Clinical Failure:** Clinical failure at TOC will be carried forward regardless of lost to follow-up.

### **9.1.3 Microbiological Outcomes per Baseline Pathogen for EOT and TOC**

The microbiological outcomes per baseline pathogen will be determined by the sponsor according to the following criteria established for each infection site at EOT and TOC. In case treatment duration is extended beyond 14 days, an additional microbiological outcome will be assessed on Day 14.

#### **9.1.3.1 HABP/VABP/HCABP**

- **Eradication:** Absence of the baseline Gram-negative pathogen from an appropriate clinical specimen. If it is not possible to obtain an appropriate clinical culture and the subject has a successful clinical outcome, the response will be presumed to be eradication.
- **Persistence:** Continued presence of the baseline Gram-negative pathogen from an appropriate clinical specimen.
- **Indeterminate:** No culture obtained from an appropriate clinical specimen or additional antibacterial therapy for the treatment of the current infection.

#### **9.1.3.2 cUTI**

- **Eradication:** A urine culture shows the baseline Gram-negative uropathogen found at entry at  $\geq 10^5$  CFUs/mL are reduced to  $< 10^3$  CFUs/mL.
- **Persistence:** A urine culture shows that the baseline Gram-negative uropathogen found at entry at  $\geq 10^5$  CFUs/mL grows  $\geq 10^3$  CFUs/mL.
- **Indeterminate:** No urine culture obtained from an appropriate clinical specimen or additional antibacterial therapy for the treatment of the current infection.

#### **9.1.3.3 BSI/Sepsis**

- **Eradication:** Absence of the baseline Gram-negative pathogen from a blood culture and/or other primary source as applicable. In the case of sepsis, if the subject has a successful clinical outcome and it is not possible to obtain an appropriate clinical culture, the response will be presumed to be eradication. In the case of BSI, if the subject has a successful clinical outcome and the investigator considers no further need to obtain a clinical culture, the response will be presumed to be eradication.

- **Persistence:** Continued presence of the baseline Gram-negative pathogen from a blood culture or other primary source.
- **Indeterminate:** No culture obtained from an appropriate clinical specimen or additional antibacterial therapy for the treatment of the current infection. The exception to this is noted in 9.1.3.3 definition of Eradication.

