### 7.11.3.3 BSI/Sepsis

- **Eradication:** Absence of the baseline Gram-negative pathogen from a blood culture and/or other primary source as applicable. In the case of sepsis, if the patient has a successful clinical outcome and it is not possible to obtain an appropriate clinical culture, the response will be presumed to be eradication.
- **Persistence:** Continued presence of the baseline Gram-negative pathogen from a blood culture or other primary source.
- **Indeterminate:** No culture obtained or additional antibacterial therapy for the treatment of the current infection including missed sampling.

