##### **9.1.4.3 BSI/Sepsis**

- **Sustained Eradication:** Absence of the baseline Gram-negative pathogen from a blood culture or other primary source after TOC as applicable. In the case of sepsis, if the subject has a successful clinical outcome after TOC and it is not possible to obtain an appropriate clinical culture, the response will be presumed to be sustained eradication. In the case of BSI, if the subject has a successful clinical outcome and the investigator considers no further need to obtain a clinical culture, the response will be presumed to be eradication.

- **Recurrence:** Recurrence of the baseline Gram-negative pathogen from a blood culture or other primary source after TOC and the TOC culture is negative.
- **Indeterminate:** No culture from an appropriate clinical specimen or subject received additional antibacterial therapy for the treatment of the current infection. Indeterminate at TOC will be carried forward. . The exception to this is noted in 9.1.4.3 definition of Eradication.
- **Persistence:** Persistence at TOC will be carried forward.

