#### 9.2.4.3 BSI/Sepsis

- **Eradication:** Absence of the baseline Gram-negative pathogen from a blood culture and/or other primary source as applicable. If the subject has a successful clinical outcome and it is not possible to obtain an appropriate clinical culture, the response will be presumed to be eradication. In the case of BSI, if the subject has a successful clinical outcome and the investigator considers no further need to obtain a clinical culture, the response will be presumed to be eradication.
- **Persistence:** Continued presence of the baseline Gram-negative pathogen from a blood culture or other primary source or death due to BSI/sepsis. If EOT is persistence, TOC is also persistence.
- **Indeterminate:** Lost to follow-up due to death not related to current infection, withdrawal, no assessment, or additional antibacterial therapy for the treatment of the current infection.

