## 15. CHANGES FROM PROTOCOL

- Add analysis for HABP/VABP/HCABP + BSI/sepsis subgroup for efficacy endpoint
- Add analysis by initial study drug regimen for clinical and microbiological outcome
- Add analysis for supplementary clinical and microbiological outcome
- Add subgroup analysis for all-cause mortality
- Add analysis for microbiological outcome by MIC and interpretation
- Add analysis for all-cause mortality for subjects with cUTI
- Add analysis for new infectionChange target timepoint of analysis window for premature EOT (PK data), from end date/time of last infusion to start date/time of last infusion since EDC does not capture end of infusion date/time for premature EOT.
- The reference point of prior/concomitant medication has been changed from randomication date to first drug infusion
- If BSI, also allowed to consider presumed eradication.
- Add imputation rule if date/time is missing (section 6.4)

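### The SAP presumes eradication in bloodstream infection (BSI) from clinical success plus the open-label investigator's view that no further culture is needed, without requiring any negative blood culture

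*SAP*

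**What the plan says.** Protocol 7.11.3.3 has one route to presumed eradication in this stratum: "In the case of sepsis, if the patient has a successful clinical outcome and it is not possible to obtain an appropriate clinical culture". Its Indeterminate category reads: "No culture obtained or additional antibacterial therapy for the treatment of the current infection including missed sampling".

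SAP 9.1.3.3 keeps the sepsis route and adds one for BSI, which applies "if the subject has a successful clinical outcome and the investigator considers no further need to obtain a clinical culture". It then takes these subjects out of Indeterminate: "The exception to this is noted in 9.1.3.3 definition of Eradication". At follow-up (FU), 9.1.4.3 repeats the rule: where "the investigator considers no further need to obtain a clinical culture, the response will be presumed to be eradication". Sections 9.2.4.3 and 9.2.5.3 carry it into the supplementary outcomes. SAP section 15 discloses the change in one line, "If BSI, also allowed to consider presumed eradication", with no culture condition and no rationale. The revision record for version 3.0 (27 June 2019) describes it as a clarification.

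Three other provisions bear on the rule:

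- Protocol 8.2.4 to 8.3 schedule blood cultures until negative at Early Assessment (EA), Day 14 (where treatment is extended), End of Treatment (EOT) and Test of Cure (TOC). At FU (8.4) cultures are taken only if indicated.
- Clinical cure in BSI/sepsis (SAP 9.1.1.3, as in the protocol) requires that bacteremia be eradicated, but does not say how this is to be shown.
- The bacteremia endpoint in SAP 9.4.1.2 borrows the criteria of 9.2.4.3 and 9.2.5.3, restricted to blood specimens.

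**The concern.** A microbiological outcome should rest on microbiological evidence, or on a stated reason why none could be obtained. The protocol's sepsis exception meets that test, because the culture was not possible. The SAP's BSI exception does not: it replaces impossibility with an opinion that further culture is unnecessary, and names no result on which that opinion must rest. The definitions can also become circular, since cure requires clearance of bacteremia and clearance may be presumed from clinical success.

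The person who decides whether to re-culture knows the treatment. If re-culturing differs between arms, eradication rates can move apart or together with no supporting culture data. What is at stake is how the BSI/sepsis microbiological outcome, the clinical-microbiological composite and possibly the bacteremia endpoint are interpreted.

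**Working it through.** **Step 1: classify three BSI subjects, each clinically cured at TOC with no TOC blood culture.**

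| Subject | Protocol 7.11.3.3, read literally | SAP 9.1.3.3 | With the proposed condition |
|---|---|---|---|
| A: blood negative at EA, so no later culture was due | Indeterminate | Eradication | Eradication |
| B: no negative blood culture on record; investigator judged no further culture needed | Indeterminate | Eradication | Indeterminate |
| C: no negative blood culture on record; sample missed by oversight, no such judgement | Indeterminate | Indeterminate | Indeterminate |

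The SAP rule is sensible for A. Only B is a problem. B can arise at TOC only if a culture that the schedule required was not taken, because blood is to be cultured until negative.

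**Step 2: consequence for subject B.**

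- Without the presumption, B is a non-responder (SAP 6.4.2), has an Indeterminate composite (Table 9-2, Indeterminate with clinical cure), and stays Indeterminate at FU: "Indeterminate at TOC will be carried forward".
- With it, B is a microbiological responder and a composite Response at TOC (Table 9-2, Eradication with clinical cure), and is no longer carried forward as Indeterminate.

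**Step 3: size of one such case.** The allocation reproduces: 150 × 2/3 = 100 on cefiderocol, as stated, leaving 50 on BAT. Protocol 3.2.1 plans 20% of patients as BSI/sepsis. Protocol 4.1 and 5.4 say only that BSI/sepsis is the remainder after about 50% pneumonia and at most 30% cUTI, so a larger share is possible. The step per case is 100/n points.

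| Scenario | Cefiderocol n | BAT n | One case, cefiderocol | One case, BAT |
|---|---|---|---|---|
| 20% share: 150 × 0.20 = 30 | 20 | 10 | 5.0 points | 10.0 points |
| 30% share (assumed): 150 × 0.30 = 45 | 30 | 15 | 3.3 points | 6.7 points |
| 20% share, 80% centrally confirmed (assumed) | 16 | 8 | 6.3 points | 12.5 points |
| 20% share, 70% centrally confirmed (assumed) | 14 | 7 | 7.1 points | 14.3 points |

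The last two rows reflect SAP 5.3, which limits the primary efficacy population to subjects whose resistant pathogen the central laboratory confirms.

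**Step 4: arm difference.** With k1 and k2 such cases at the 20% share, the difference shifts by k1/20 − k2/10. Equal proportions cancel: 2/20 − 1/10 = 0. The sign depends on which arm has more.

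**Step 5: context.** Assume 10 documented eradications among 20 cefiderocol subjects. The rate is 50.0% (Clopper-Pearson 95% CI 27.2 to 72.8). Two presumed cases make it 60.0% (36.1 to 80.9).

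**Step 6: bacteremia endpoint.** The restriction to blood specimens in 9.4.1.2 could mean that a blood result is required, which disables the presumption, or only that other specimens are ignored, which leaves it in force. The SAP does not say which. This endpoint spans all infection sites and its denominator is not given, so no step size is calculated.

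**The case against.** The strongest reply is that the rule repairs a real conflict in the protocol. Subject A has no later blood culture by design, yet Protocol 7.11.3.3 read literally makes that patient a non-responder. Read with the schedule, a judgement that no further culture is needed most naturally follows a negative result. BSI clinical cure already requires clearance, the sponsor rather than the site determines the per-pathogen outcome (SAP 9.1.3), and the change is disclosed. All of this stands, and it makes subject B uncommon if the schedule is followed. But none of it is a condition of the rule, and the sponsor's determination applies the same criteria.

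It is also fair to say that pneumonia and sepsis keep a presumption without a negative culture. There, in the primary definitions, the trigger is that a culture cannot be obtained; only BSI turns on a view that one is unnecessary.

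A reader might infer more than the documents support:

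- *Every missed BSI culture becomes an eradication.* No. Clinical success and the investigator's judgement are both needed, and subject C stays Indeterminate.
- *The SAP dropped the protocol's mention of missed sampling in order to loosen BSI.* No. It is dropped for all three infection types, and the no-culture wording that remains still covers missed samples.
- *The BSI sentence in pneumonia section 9.2.4.1 and the sepsis qualifier absent from 9.2.4.3 are proven errors.* No. Section 9.2.4.3 does begin without that qualifier: "If the subject has a successful clinical outcome and it is not possible to obtain an appropriate clinical culture, the response will be presumed". But bacteremia secondary to pneumonia is classed under pneumonia (Protocol 4.1), and section 9.2 differs deliberately from 9.1 elsewhere. Either could be intended.

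**Conclusion.** The point holds as a gap in a definition. The four SAP sections let a BSI subject with no documented clearance count as eradicated, where the protocol would score Indeterminate. Neither the culture schedule nor the cure definition closes the gap.

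The reach is limited. A reader might infer that the primary result is compromised, but the BSI/sepsis primary endpoint is clinical outcome at TOC (SAP 9.3), and the presumption is not written into its definition. The affected outcomes are secondary rates reported with confidence intervals and no between-arm test. Nor do the documents support a claim that the rule favours cefiderocol.

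One case is worth about 5 points (cefiderocol) or 10 points (BAT) at the planned 20% share, 3.3 or 6.7 at an assumed 30% share, and more if fewer subjects are centrally confirmed. The number of cases is not given anywhere, so the total effect cannot be stated. The rule covers BSI only, so fewer subjects than the whole BSI/sepsis stratum can be affected. The correction is worth making because it is cheap and uses cultures already collected.

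**What to change.** 1. In SAP 9.1.3.3, 9.1.4.3, 9.2.4.3 and 9.2.5.3, allow presumed eradication in BSI only when a blood culture taken after the last positive one is documented negative for the baseline pathogen and no later blood culture is positive. Otherwise score Indeterminate. Anchoring on the last positive culture, rather than on any post-baseline culture, protects a subject who qualified on an earlier specimen (Protocol 7.7.1 and SAP 6.5 allow this) and was already negative before treatment.
2. In 9.4.1.2, state that the bacteremia endpoint needs such a documented negative blood culture.
3. Report documented and presumed eradication separately by arm in the existing tables.
4. Ask the sponsor what was intended by the BSI sentence in 9.2.4.1 and by the missing sepsis qualifier in 9.2.4.3. Do not delete or restore either automatically.
5. Leave the primary clinical-cure definition unchanged.

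The cost is SAP wording in five sections, one split in existing tables and one query to the sponsor. No new sampling is needed. The downside is that a few BSI subjects without documented clearance move to Indeterminate and count as non-responders. Patients whose blood cleared early keep their eradication.
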